5.1 Primary objectives

The primary objective of VESPER is to evaluate the clinical and cost-effectiveness (using the outcomes listed in 5.3) of two experimental interventions for women with refractory rUTI: intravesical gentamicin; Intravesical GAG replacement; and compare to the control arm of antibiotic prophylaxis (second-line prophylactic daily oral antibiotics [comparator arm]).

5.2 Secondary objectives

The secondary objectives are to evaluate the clinical, economic and safety outcomes listed in 5.4, and to provide a qualitative process evaluation to explore trial processes, intervention mechanisms, and context to inform further implementation

5.3 Primary outcomes measure(s)

The primary clinical effectiveness outcome is the rate of symptomatic, antibiotic-treated UTI, selfreported by participants from randomisation to the 6-month treatment period (verified from medical records).

The primary economic outcome is the incremental cost per quality-adjusted life year (QALY) gained, based on responses to EQ-5D-5L, over 12 months.

5.4 Secondary outcomes measure(s)

Secondary outcome measures include:

- Occurrence of symptomatic UTI in months 6-12 (following treatment completion)
- Psychosocial burden of rUTI using the rUTI Impact Questionnaire¹¹ at 6 months and 12 months

- Antibiotic use: number of courses of antibiotics prescribed for UTI
- Microbiologically proven UTIs: defined as per the primary outcome plus a concomitant positive urine culture (central laboratory). Participants will be requested to submit urine samples both locally and to the central laboratory when they suspect a UTI based on symptoms. A positive culture will be classified according to UK Health Security Agency (UKHSA) standards for Microbiological Investigations (SMI) B41: Investigation of urine definitions²⁵.
- AMR in *E. coli* isolated from urine or perineal swabs.
 - Ecological change in terms of bacterial species plus antimicrobial resistance patterns from i) mid-stream urine and ii) faecal reservoir (via optional perineal swabs) during the 6-month treatment period and in the 6 months following completion of treatment. Urine and optional perineal samples will be taken at hospital visits during both treatment and follow-up, plus participants will be requested to submit further urine samples to the central laboratory when they suspect a UTI based on symptoms. GP or hospital records will be checked to confirm any additional urine culture results, including resistance patterns of the bacteria cultured. We are planning to longitudinally monitor development of antimicrobial resistance in the primary uropathogen *E. coli* isolated from urine by collecting specimens sent by participants directly to our central reference laboratory at the time of each UTI and during asymptomatic periods at baseline, 1,3, 6 and 12 months. We will also assess resistance pattern change in *E. coli* within the faecal reservoir by obtaining isolates from perineal swabs sent at baseline, 6 and 12 months.
 - Multi-drug resistance in *E. coli* isolated from urine or perineal swabs, defined as resistance to >=1 antimicrobial agent in >=3 antibiotic categories
- Bacterial species or antibiograms most commonly associated with recurrent UTI.
- Asymptomatic bacteriuria defined as a positive urine culture without symptoms
- Adherence with allocated treatment (patient reported)
- Adverse events
- Hospitalisation due to UTI

• Costs to NHS and personal social services (PSS) at 12 months and modelled over participant lifetime

VESPER

- QALYs at 12 months based on completion of the EQ-5D-5L at baseline,3 ,6, & 12 months and modelled over participant lifetime.
- Incremental cost per QALY gained at 6 months.
- Incremental cost per QALY gained over a lifetime horizon.
- Willingness-to-pay (WTP) for the interventions' attributes and to avoid a UTI estimated from responses to a discrete choice experiment (DCE) at 13 months
- Participant satisfaction measured using the Treatment Satisfaction Questionnaire for Medication at 6 and 12 months.
- Understanding of contextual factors influencing adherence, acceptability and implementation of intervention.

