We will use a Sequential Multiple Assignment Randomised Trial (SMART) design²⁹. This enables women to be re-randomised to a different prophylactic regime if they do not respond to their initially allocated prophylaxis. This will allow us to explore the optimal sequence of prophylaxis regimens. We will define relapse as at least two episodes of UTI occurring in the 6-month treatment period in line with currently accepted definitions of recurrent UTI. All women will have a fixed 12-month post randomisation trial period. If a participant is re-randomised to a different arm, their treatment will start back to time zero ie if a participant gets re-randomised at the end of their 6-months treatment period, they would be on the new treatment for a further 6-months.

Our target population are adult (\geq 16 years) women with a documented history of recurrent uncomplicated UTI, for whom second-line treatments would be considered e.g. at least three episodes of symptomatic antibiotic-treated urinary infection in the previous 12 months or two episodes of UTI

Canolfan

in the last 6 months despite the use of first line treatments such as intravaginal oestrogen, the oral urinary antiseptic methenamine Hippurate or first-line low dose oral antibiotics.

Whilst the main mode of data capture will be electronic, we will provide alternatives for participants either on paper or by telephone. Urine and optional perineal swab samples will be taken at baseline and at subsequent hospital visits during both treatment and follow-up periods (12 months in total). Participants will also be requested to submit further urine samples to the central laboratory when they suspect a UTI based on their symptoms. Participants will be provided with the central laboratory address together with all sample collection materials that are needed.

Central laboratories contact details:

[name]

Specialist Antimicrobial Chemotherapy Unit,

Public Health Wales,

University Hospital of Wales,

[name],

[name]

The trial is a UK multi-centre trial involving 20 secondary care NHS organisations.

6.1 Adherence data:

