For those women randomised to receive oral antibiotics, a second line once-daily prophylactic low dose will be prescribed for 6 months. The agent to be used will be active against common urinary pathogens and selected by the responsible clinician depending on patient characteristics such as previous use, allergy, renal function, prior urine cultures and local guidance. Current NICE guidelines suggest use of nitrofurantoin 50 mg or 100 mg, trimethoprim 100 mg, or cefalexin 125 mg or 250 mg can be used. Renal function will be determined by eGFR at baseline and if this is less than 45 ml/min nitrofurantoin will not be used. Liver function tests will be monitored throughout the trial as some of the antibiotics, particularly nitrofurantoin, require this. Participants will be asked to take the oncedaily antibiotic prophylaxis as a single dose at bedtime. If there are specific and/or intolerable adverse effects such as nausea with nitrofurantoin, or candidiasis with cefalexin then changing to an alternative oral antibiotic agent would be advised in consultation with the relevant clinician with the reasons for the change recorded. The aim will be to maintain participants on oral antibiotic prophylaxis for as long as possible during the 6-month treatment period within tolerance and safety constraints. Participants intolerant of prophylactic antibiotics despite trying alternative agents will have the opportunity to discontinue the medication and be offered an alternative treatment which will include intravesical treatments. This information will be recorded, and the participant will continue on in the study. If a participant in the prophylaxis group develops symptoms and signs suggestive of

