11.12 Accountability procedures

No medications or associated equipment or consumables are being provided to sites as part of the trial, and therefore, sites are expected to use their own stock. No CTR accountability, recall and disposal procedures are required as described in the VESPER safety Management Plan.

Continuation of the treatments after completion of the 6-month treatment period is not recommended. Following the 6-month treatment period, any additional care, during the 6-month follow up period and beyond is not expected to differ from what is normally expected for patients with recurrent UTIs. It is usual for a period of observation to be undertaken after completion of a period of preventative treatment and the minimum period for this is usually 3 months. Participants will be encouraged to continue without UTI prevention for 6 months following completion of the

intervention but in some cases this may not be possible. If preventative treatment is restarted before the end of the scheduled 6 months post-treatment observation period, then this will be recorded.

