A positive culture will be classified according to UK Health Security Agency (UKHSA) standards for Microbiological Investigations (SMI) B41: Investigation of urine definitions.

Mid-stream urine samples that are being sent to the central laboratory will be collected in appropriately trial labelled sterile 30ml Universal containers containing boric acid. Boric acid will preserve the sample by inhibiting bacterial growth and maintaining the sample's integrity during transport and storage. The urine sample will be transported to the central laboratory in SpeciSafe® transport containers and mailing envelopes which are compliant with UN3373 Regulations for Cat B biological samples.

Urine samples should arrive at the central laboratory as soon as possible.

Perineal swabs (swab with amies transport medium) will be used to collect faecal samples at baseline and at 6 and 12-month follow-up timepoints. Swabs will be returned to the central laboratory in UN3373 regulatory compliant mailing envelopes for Cat B biological samples.

Perineal swabs should arrive at the central laboratory within as soon as possible.

Processing and storage of the urine and perineal samples sent to the central laboratory will be performed according to the VESPER Sample Management and Laboratory Manual.

Processing, analysing and storage of urine and perineal samples will be performed as per section 16.4: Briefly, urine samples will undergo automated microscopy and culture for urinary pathogens according to SMI: B41. Uropathogens will be susceptibility tested using the current standardised EUCAST methods and guidelines.

13 **Trial procedures**

All participants will be enrolled in the trial for 12-months; 6-months intervention period followed by 6-months follow-up period.

The primary clinical outcome will be assessed at the end of the 6-months intervention period and the primary economic outcome will be assessed over the subsequent 6-months follow-up period.

Secondary outcomes will be measured at the end of the 6-months and 12-month periods.

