- Population-level summary: Incidence rate ratio from Poisson or negative binomial regression model for intravesical treatments and second-line oral antibiotic prophylaxis arms.

Rationale for estimand: To compare the strategy of initially prescribing intravesical treatments compared to prescribing second-line oral antibiotic prophylaxis as would be observed in routine practice.

Sensitivity analyses around the primary outcome will consider appropriate estimands, accounting for initial allocation and reinstatement/switching of different prophylaxes via the SMART design. Weighted and replicated regression approach will be considered to evaluating adaptive intervention effects³⁴.

Secondary outcomes will also be analysed based on intention-to-treat using appropriate regression models (e.g. linear regression for continuous outcomes, Poisson/negative binomial for counted outcomes, logistic regression for binary outcomes, as appropriate), adjusting for covariate factors

used in randomisation as per the primary analysis, and are described in the Table below. Mixed-effects models will be considered when participants have multiple data points over time.

As part of our process evaluation, we will describe differences between those who opt for different modes of intravesical administration (i.e. self vs clinician-delivered), including the extent to which it varies across sites. We will also describe the timing of this decision in relation to randomisation and whether this is associated with differential response, switching, and outcomes. We will similarly describe the variability (and association with response/outcomes) in prophylaxis implementation more generally (i.e. which oral antibiotics are used in the oral antibiotic arm, switches and circumstances around switching etc.)

Table 7 - planned outcome analysis

Outcome	Measure	Time frame	Analysis
Occurrence of symptomatic UTI in the 6-month follow-up period	UTI-rate occurred after 6 months of treatment period	At 12 months	Poisson/ negative regression
Change in rUTI Impact Questionnaire	Recurrent UTI impact questionnaire	At 6 months/12 months	Linear regression
Days prescribed antibiotics	Addition antibiotic prescribed	At 6 months/12 months	Poisson/ negative regression
Microbiologically proven UTIs	Per the primary outcome plus a concomitant positive urine culture	At 6 months/12 months	Logistic regression

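### The months 6-12 UTI outcome is labelled post-treatment, yet re-randomised women are on second-stage treatment then, so the comparison by initial arm is one of strategies and can favour the worse arm

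*Protocol*

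**What the plan says.** **Months 6-12 as post-treatment.** Section 5.4 lists "Occurrence of symptomatic UTI in months 6-12 (following treatment completion"). Table 7 in 16.1 gives the measure as "UTI-rate occurred after 6 months of treatment period", assessed at 12 months with a count regression. Secondary outcomes are analysed by intention to treat. Section 13 applies one structure to everyone: "All participants will be enrolled in the trial for 12-months; 6-months intervention period followed by" six months of follow-up. Section 20 repeats it, and the synopsis describes the second half-year as coming after the allocated treatment is complete. Section 11.12 adds: "Participants will be encouraged to continue without UTI prevention for 6 months following completion of the" intervention. It accepts that this will not always be possible and asks that restarts be recorded.

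**Months 6-12 as treatment.** Sections 6 and 9.6.2 reset the treatment clock on re-randomisation. Their example is a woman who is "re-randomised at the end of their 6-months treatment period, they would be on the new treatment for a further 6-months". Section 6 fixes the trial period at 12 months from first randomisation. Section 15.1 sets the efficacy trigger at two or more UTIs in the treatment period, with 1:1 re-randomisation between the other two arms.

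**Sequence analysis.** Section 16.1 states: "Sensitivity analyses around the primary outcome will consider appropriate estimands, accounting for initial allocation and reinstatement/switching" between prophylaxes, and then names weighted and replicated regression as a method to be considered. The primary outcome runs from randomisation to six months. The exploratory sequence outcome in 5.5 has no stated window.

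**The concern.** Six months of first treatment, six of second treatment and six of untreated follow-up do not fit into 12 months. For a woman re-randomised at month 6, the whole supposed post-treatment window is on treatment. For one re-randomised at month t before 6, treatment runs to month t+6.

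The share of women affected will differ by arm, because the main trigger is failure on the same kind of event that the outcome counts. The worse first arm has more women under active prophylaxis in months 6-12, and this lowers its UTI rate there. Someone reading the label would take the result as evidence on whether protection lasts after treatment stops. It could point the wrong way.

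The sequence analysis has a matching window problem. Within 0-6 months, a second stage that starts at month 6 contributes nothing, and an earlier switch contributes only the time left to month 6.

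**Working it through.** The conflict of wording needs no arithmetic. The plan gives no figure for this bias, so the following only illustrates its direction and size.

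**Inputs from the protocol**
- UTI rates of 2 (oral) and 1 (intravesical), from 15.3. The time unit is not stated with these rates, but the rationale speaks of one episode per year. Both readings are shown: 2 vs 1 per six months, and 1 vs 0.5 per six months (the per-year reading).
- Trigger of two or more UTIs, and 1:1 re-randomisation (15.1).
- About seven UTIs a year in women with recurrent UTI (section 4), that is 3.5 per six months, as the top off-treatment rate.

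**Assumptions**
- The off-treatment rate c is the same in all arms, 1 to 3.5 per six months, so the true post-treatment ratio is 1.00.
- Uptake of re-randomisation is 100% or 50%.
- Counts are Poisson. Intolerance and third-arm switches are ignored.

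**Step 1: share meeting the trigger.** P = 1 − e^(−r)(1 + r).
- r = 2: 59.4%
- r = 1: 26.4%
- r = 0.5: 9.0%

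**Step 2: second-stage rate.** Oral failures go to one of the two intravesical arms, so their rate is 1. Intravesical failures go half to oral and half to the other intravesical arm: (2 + 1)/2 = 1.5. On the per-year reading the rates are 0.5 and 0.75.

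**Step 3: months 6-12 rate by initial arm, switching at month 6.** Rate = (1 − P) × c + P × second-stage rate. With 2 vs 1 and c = 2:
- oral: 0.406 × 2 + 0.594 × 1 = 1.41
- intravesical: 0.736 × 2 + 0.264 × 1.5 = 1.87
- ratio: 1.868/1.406 = 1.33

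**Step 4: switching at the second UTI.** A woman whose second UTI comes at fraction u of the first six months is treated for fraction u of months 6-12. The expected treated share is the integral of r²u²e^(−ru) over u from 0 to 1: 0.323 (r = 2), 0.161 (r = 1) and 0.058 (r = 0.5). This share replaces P in step 3.

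**Results: intravesical/oral ratio when the truth is 1.00**

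| Rates per 6 months | Switch | Uptake | c = 1 | c = 2 | c = 3.5 |
|---|---|---|---|---|---|
| 2 vs 1 | month 6 | 100% | 1.13 | 1.33 | 1.47 |
| 2 vs 1 | month 6 | 50% | 1.07 | 1.14 | 1.17 |
| 2 vs 1 | second UTI | 100% | 1.08 | 1.14 | 1.18 |
| 1 vs 0.5 | month 6 | 100% | 1.13 | 1.18 | 1.20 |
| 1 vs 0.5 | month 6 | 50% | 1.06 | 1.08 | 1.09 |
| 1 vs 0.5 | second UTI | 100% | 1.07 | 1.10 | 1.11 |

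Simulation of the full-uptake rows with 400,000 women per arm agrees to within 0.01. Adding gamma variation between women (dispersion 0.5 or 1) raises the month-6, full-uptake ratios to 1.20-1.52 over both readings.

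**Step 5: a true lasting 30% intravesical benefit (ratio 0.70), month 6, full uptake, c = 2 for oral and 1.4 for intravesical.**
- 2 vs 1: (0.736 × 1.4 + 0.264 × 1.5)/1.406 = 1.426/1.406 = 1.01. The benefit disappears.
- 1 vs 0.5: (0.910 × 1.4 + 0.090 × 0.75)/1.604 = 1.341/1.604 = 0.84. The benefit shrinks but keeps its direction.

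With a true ratio of 0.50 the results are about 0.80 and 0.61.

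**The case against.** The strongest reply is that nothing is biased, because the protocol does not claim an off-treatment estimand. Secondary outcomes are analysed by intention to treat, the primary estimand is treatment policy with switching included, and 11.12 foresees that some women restart prevention. Table 7's wording can be read as a calendar window. This stands in part: months 6-12 by initial arm is a legitimate comparison of strategies. It does not rescue 5.4, which places the outcome after treatment completion, or section 13, which gives everyone the same two halves.

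The size is also conditional. The largest ratios need the per-six-month reading, a wait until month 6 and full uptake, whereas the protocol says only that women can be re-randomised and its rationale is per year. Reversal is not certain when a large benefit persists. All of this stands.

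Three stronger readings are tempting but unsupported:
- *The best-sequence objective cannot be answered.* Section 5.5 sets no window, month 6 is only an example, and earlier switchers do contribute second-stage time. The SAP could set 0-12 months. What can be said is that the one named method is attached to a 0-6 month outcome.
- *Section 15.1 re-randomises intolerant women only for antibiotic side effects.* Its list is introduced as inclusive. Section 9.6.2 allows re-randomisation for intolerable side effects generally, while 11.1 says that women intolerant of oral agents will "be offered an alternative treatment which will include intravesical treatments" and uses similar wording for the intravesical arms. These passages should be reconciled; they do not show that the 1:1 probability fails for women actually re-randomised.
- *A weighted analysis of post-treatment time would recover durability.* If every failure switches at month 6, failures have no untreated time to weight up. The women left are selected on outcome. With rates 2 vs 1, no true off-treatment difference and gamma variation between women, the ratio among women with fewer than two UTIs is 0.80/0.625 = 1.28 (dispersion 0.5) or 0.667/0.467 = 1.43 (dispersion 1), as large as the problem being corrected.

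**Conclusion.** The definition in 5.4 is wrong as written: it contradicts the re-randomisation rule in sections 6 and 9.6.2 within a fixed 12 months. That part rests on the text alone. The comparison in Table 7 is valid for initial strategies but is not a post-treatment effect, and it *can* favour the worse initial arm; to say that it will do so would be too strong.

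With no true off-treatment difference and Poisson counts, the distortion is about 1.06-1.20 on the per-year reading, with early switching, or with half uptake. Ratios of 1.33-1.47 need 2 vs 1 per six months, off-treatment rates of 2-3.5 and universal switching at month 6. Variation between women would raise the month-6 figures. Off-treatment rates and uptake are assumptions. The sequence limb is weaker: the named analysis is poorly placed, but the objective remains answerable.

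**What to change.** 1. In 5.4 and Table 7, define the outcome as *UTI rate in months 6-12 by initial allocation, including any re-randomised treatment*, and remove the reference to treatment completion. Align the descriptions of the second half-year in the synopsis and sections 13 and 20. Draw no post-treatment durability conclusion from this outcome, and report by arm the person-time on second-stage treatment in months 6-12.
2. Evaluate treatment sequences on the 0-12 month UTI rate, applying the 1:1 weights only to women actually re-randomised.
3. Give any post-treatment rate among women never re-randomised as descriptive only.
4. Reconcile what 9.6.2, 11.1 and 15.1 say about intolerant women.

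Items 1-3 cost protocol and SAP wording plus one extra table; they change no visit, treatment or sample size. The price is that the trial gives up a randomised statement on durability, which the present design does not provide.

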analysis identified no randomised trials (RCTs) of intravesical antibiotics and two small RCTs for intravesical GAG replacement compounds (n=26, n=54)⁹. Despite this paucity of high-level evidence our recent survey conducted via the UK Continence Society found that 76% of specialists regularly use intravesical treatments in their everyday practice. There appears to be a significant disparity between the widespread clinical use of these treatments and the evidence required to justify this. A recent overview in this topic area highlighted the use of intravesical preventative treatments as a potential future therapy and stated that "high local concentrations of antibiotic at the urothelial surface can be achieved by direct instillation into the urinary tract". The authors noted that "only the performance of clinical trials in the appropriate patient populations can properly appraise the potential of intravesical therapy for UTI"¹⁰. There is clearly an urgent need for a well-designed trial to demonstrate the relative effectiveness of the 2 most commonly used intravesical treatments and compare this to the current guideline-recommended treatment of second line daily oral antibiotics. VESPER, a 3-arm RCT designed to assess the relative effectiveness and cost-effectiveness of two intravesical preventative treatments, Gentamicin and GAG replacement compounds, against guidelinerecommended second-line daily oral tablet antibiotic prophylaxis will directly address this evidence gap. Secondary outcomes will include development of antimicrobial resistance (AMR) during treatment, total antibiotic use, patient-reported treatment satisfaction, patient-reported UTI impact¹¹, adverse events and, using economic analysis, the value of the interventions to women suffering rUTI and to the NHS.

4.1 **Rationale for current trial/Justification of Treatment Options**

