VESPER is directly aimed at infection prevention. The incidence of AMR within post-menopausal rUTI sufferers increases from 25% to >80% following prolonged antibiotics¹⁶. A systematic review and meta-analysis¹⁷ (searches up to 2009) identified a number of studies that together provide strong evidence of an association at the individual patient level between the prescribing of antibiotics in primary care and antimicrobial resistance in bacteria at different sites, including urinary tract infections, with effects lasting up to 12 months. The UK AMR strategy highlights that "we are heading rapidly towards a world in which antibiotics no longer work" due to "increased and inappropriate use" and advises that "preventing infections is essential"¹³. A recent publication details an estimated 4.95M deaths associated with AMR globally in 2019¹⁸. Urinary Tract Infections (UTIs) caused by antibioticresistant bacteria are difficult to treat and often recur. They also account for a staggering 50% of all known cases of sepsis¹³. For example, unplanned hospital admissions secondary to UTIs cost £434 million in 2013/2014. The frequent UTI sepsis complication is well-recognised and is noted within the NHS Long Term Plan as a key problem to be tackled. The goal is to reduce Gram-negative sepsis by 2024/25 and focus on UTIs as they are a leading cause of bloodstream infections¹⁹. The key causative organisms of both UTIs and urosepsis are *E. coli* (~50%) and Klebsiella (~15%)²⁰. Worryingly, extendedspectrum Beta-Lactamase (ESBL) producing *E. coli* and Klebsiella species are increasingly common, and are included in the World Health Organisation 'priority pathogens' list²¹.

VESPER is designed to demonstrate treatment superiority in terms of UTI reduction. The two experimental interventions in our study both have potential to reduce AMR by limiting UTI occurrence and consequent systemic antibiotic exposure which would be a major benefit to public health. Although one experimental arm is an antibiotic, it is unlikely to affect the gut flora as it is administered directly into the bladder and not absorbed systemically due to the low permeability of the urothelium which lines the urinary tract. Previously published work from co-applicants has shown that gentamicin is undetectable in the bloodstream of patients who receive it intravesically.^{22, 23}.

Canolfan

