11.3 Treatment prescribing and dispensing

Treatment will be prescribed and dispensed following local procedures. Gentamicin and GAG should be ordered through inpatient supply route and oral antibiotics should be ordered through outpatient pharmacy. Prescriptions for antibiotics are to be prescribed at randomisation, month 1 and month 3.

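### Antibiotic use is defined in three incompatible ways, and the definitions that would be analysed leave out oral prophylaxis, so the promised total antibiotic use is not measured

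*Protocol*

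**What the plan says.** The protocol describes the antibiotic-use outcome in three places.

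- **Section 4, Background**, lists among the secondary outcomes "development of antimicrobial resistance (AMR) during treatment, total antibiotic use".
- **Section 5.4** defines it as "Antibiotic use: number of courses of antibiotics prescribed for UTI", with no time window.
- **Section 16.1, Table 7**, names the row "Days prescribed antibiotics" and the measure "Addition antibiotic prescribed" (apparently meaning additional), analysed at 6 and 12 months by Poisson or negative binomial regression.

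Section 11.1 uses the word course for the discrete treatment of a breakthrough UTI. It keeps this apart from the once-daily prophylaxis of the oral arm, which lasts 6 months, is paused during a treatment course and then restarts. Section 11.3 adds "Prescriptions for antibiotics are to be prescribed at randomisation, month 1 and month 3".

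The primary outcome (section 5.3) is "the rate of symptomatic, antibiotic-treated UTI" from randomisation to 6 months. On purpose, section 4.1 says that the two intravesical treatments "both have potential to reduce AMR by limiting UTI occurrence and consequent systemic antibiotic exposure". Section 26 tells policy makers that the aim is to lower systemic antibiotic prescribing by offering other prophylactic options.

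**The concern.** The three descriptions cannot all be followed. One is a count of courses, one is a number of days, and one is a total. The first is restricted to antibiotics for UTI episodes, and the second is most naturally read as antibiotic on top of the allocated prophylaxis. Only the third would include the daily oral antibiotic.

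Daily oral antibiotic is the comparator treatment, so it is the largest source of systemic antibiotic in the trial. It is not confined to one arm. Women who relapse or cannot tolerate treatment may be re-randomised 1:1 to the two remaining regimens and may later switch to the third (sections 9.6.2 and 15.1). Preventative treatment may also be restarted in months 6 to 12 (section 11.12). None of this enters the outcome as section 5.4 defines it.

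At stake is whether the trial can make the between-arm comparison of total consumption that the Background announces. An oral-arm woman and an intravesical woman with the same number of treated UTIs would have the same course count, whatever prophylaxis each had taken.

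**Working it through.** The protocol states no figure for antibiotic exposure, so there is none to reproduce. The check is the share of oral-arm antibiotic days that a treatment-only measure leaves out.

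**Inputs**

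- Prophylaxis period: 6 months, taken as 182 days (section 11.1).
- Prophylaxis is paused during a treatment course, so the two kinds of day do not overlap (section 11.1).
- UTIs per 6 months, *m*. Section 15.3 assumes an oral-arm rate of 2 without a time unit: *m* = 2 if it is per 6 months, *m* = 1 if it is per year. As a high value, section 4 cites about seven episodes a year, so *m* = 3.5.
- Course length, *L*: not in the protocol. Assumed, with a range of 3 to 14 days.

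**Months 0 to 6, full adherence, no switching.** Share missed = (182 − *mL*)/182.

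| *m* | *L* = 3 | *L* = 7 | *L* = 14 |
|---|---|---|---|
| 1 | 179/182 = 98.4% | 175/182 = 96.2% | 168/182 = 92.3% |
| 2 | 176/182 = 96.7% | 168/182 = 92.3% | 154/182 = 84.6% |
| 3.5 | 171.5/182 = 94.2% | 157.5/182 = 86.5% | 133/182 = 73.1% |

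**Months 0 to 12, same UTI rate, no prophylaxis after month 6.** Treatment days double to 2*mL*, so the share is (182 − *mL*)/(182 + *mL*). For *m* = 2: 176/188 = 93.6% (*L* = 3), 168/196 = 85.7% (*L* = 7), 154/210 = 73.3% (*L* = 14).

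**Oral prophylaxis ends at the second UTI.** Two UTIs in the treatment period is the relapse criterion for re-randomisation (sections 6 and 15.1). If UTIs are Poisson with mean *m*, the expected fraction of the period before the second UTI is *f* = (1 − e^−*m*)/*m* + [1 − e^−*m*(1 + *m*)]/*m*. For *m* = 2, *f* = 0.729. With prophylaxis days of about *f*(182 − *mL*), the share is 95.5% (*L* = 3), 89.7% (*L* = 7) and 80.0% (*L* = 14).

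**Overlap with the primary outcome.** Each primary event carries at least one course. If UTIs are Poisson and each has an assumed probability *q* of a second course, the correlation between courses and UTIs is (1 + *q*)/√(1 + 3*q*): 1.00 at *q* = 0, 0.965 at 0.1, 0.949 at 0.2 and 0.943 at 0.3. This concerns months 0 to 6. Over 12 months the count also follows the secondary UTI outcome for months 6 to 12.

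**Does allocation alone settle prophylaxis exposure?** Take a mean of 1 UTI per 6 months in an intravesical arm (the section 15.3 value, time unit again assumed). The Poisson probability of two or more is 1 − 2e^−1 = 26%. About a quarter of those women would then qualify for re-randomisation, half of them to oral antibiotics if all took it up. Exposure by initial allocation therefore has to be measured.

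**The case against.** **Allocated treatment is not an outcome.** Six months of daily antibiotic is the oral-arm intervention. Adding those days gives a contrast driven largely by allocation, and it could swamp the treatment-course difference that randomisation can reveal. This stands in part. It is a good reason to keep treatment use as its own compared component and never to show the total alone. It does not reconcile the three definitions, and re-randomisation, switching and restarts mean that the total is not known in advance.

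**The rationale concerns treatment courses.** Section 4.1 speaks of exposure that follows from UTIs, which a course count does capture. That is a fair reading of that sentence. The promise of total use in section 4 and the aim in section 26 go further.

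**Stewardship is covered elsewhere.** A reader might infer that the trial cannot address stewardship at all. The protocol does not support that. Resistance and multi-drug resistance in *E. coli* are secondary outcomes with planned analyses. Section 16.1 commits to describing which oral antibiotics are used and the switching between regimens. These cover part of the question, but they do not compare total consumption between arms.

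**The numbers can be pushed too far.** With two UTIs in each woman and 7-day courses, one might set 182 antibiotic days in the oral arm against 14 in an intravesical arm. That needs full adherence and no switching, yet two UTIs is the trigger for re-randomisation. Nor is nine-tenths a figure from the protocol, since it rests on an assumed course length and a rate with no time unit.

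**The outcome is not a copy of the primary.** Treatment may be repeated within an episode, the analysis also runs to 12 months, and a measure in days would add duration. So it tracks the primary closely over months 0 to 6 but does not duplicate it.

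**Conclusion.** The inconsistency is plain on the page: courses for UTI in section 5.4, days of apparently additional antibiotic in Table 7, total use in section 4. Excluding oral prophylaxis follows directly from section 5.4 read with section 11.1. For Table 7 it rests on reading the garbled measure cell as additional, which is the natural reading but not a certain one.

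On those definitions the outcome does not deliver the total use announced in section 4. The share of oral-arm antibiotic days missed is about 92% to 98% for 1 to 2 UTIs in 6 months, courses of 3 to 7 days and no switching. It falls to about 73% with 14-day courses and either 3.5 UTIs in 6 months or a 12-month window at 2 UTIs per 6 months. Most exposure is missed in every case examined, so the conclusion does not hang on one percentage.

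The primary analysis is unaffected. The point should be put right because the comparison of total consumption is otherwise not prespecified.

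**What to change.** Use one definition in section 4, section 5.4 and Table 7:

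- **Total systemic antibiotic days per woman**, over months 0 to 6 and 0 to 12, by initial allocation, always shown split into prophylactic and treatment days. Prophylactic days include those after re-randomisation, switching or restart.
- **Treatment courses for UTI**, kept as a separate component and compared between arms.
- **Intravesical gentamicin instillations**, reported separately, since the protocol regards them as not systemically absorbed.

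Correct the wording of the Table 7 measure at the same time.

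The cost is wording and one derived variable. The sources are already planned: trial prescriptions (section 11.3), agent and duration of each treatment course (section 11.1), adherence forms and 12-month extraction of antibiotic prescriptions from GP or hospital records (section 13.1.3), and recorded restarts of prevention (section 11.12). The drawback is that the total is driven largely by allocation, so it must be read beside the treatment-only component.
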